6.2.2 Device Performance During Event

It is not expected that any subject will experience an arrhythmic event due to the low number of subjects that will be enrolled and the low frequency with which they occur in this patient population. However, if a subject does receive treatment from the device, the associated SWD 1000 treatment sequence performance variables will be investigated. Appropriate device response to an event will be evaluated based on:

- The device's ability to appropriately define the cardiac rhythm. Trained ECG reviewers will be used to manually assess the ECG signals and determine if the device accurately defined the rhythm.

- The subject's state of consciousness at the time the event was treated (if the SWD 1000 delivered treatment). Consciousness will be determined based on when the subject stopped using the device's response button and interviewing the patient and bystanders, if present at the time the event.
- The subject's transthoracic impedance detected during treatment (if the SWD 1000 delivered treatment)
- The energy delivered by the SWD 1000 during treatment (if the SWD 1000 delivered treatment)
- The subject's post-treatment cardiac rhythm (if the SWD 1000 delivered treatment)

All subject's receiving treatment from the device will be followed up promptly to establish the context of the event. Contextual information will be used to supplement the device-reported information. If the subject or caretaker is able to provide contextual information, it will be used to further assess subject activity at the time of treatment, subject consciousness at the time of treatment, subject perception of the treatment alarm sequence, and subject interactions with the device during the event.

There is no study endpoint associated with the review of these data.

7. RISKS AND BENEFITS

Excluding false shocks resulting from supraventricular tachycardia, there is risk of an inappropriate shock from ECG signal noise. Using non-adhesive electrodes with the commercial outpatient wearable cardioverter-defibrillator, this risk is less than one per 100 months of patient use. Other than being painful and startling, an inappropriate shock should not be life threatening or have serious effects. However, in a small percentage of cases, a false shock will induce VT or VF. If the SWD 1000 does not automatically convert an induced VT or VF, the result may be permanent disability or death.

The SWD 1000 may fail to detect an episode of VT/VF or, having detected the arrhythmia, fail to convert the VT/VF. In the event that a care taker is not capable of providing emergency resuscitation (i.e. CPR) or cannot summon emergency responders to arrive in a timely fashion, the result may be permanent disability or death.

If the subject experiences SCA due to bradycardia or asystole, the SWD 100 will alarm to notify bystanders to call for help and perform CPR, but will not provide any treatment. If the event were to occur with a hospitalized patient, medical personnel would be available to recognize the condition and respond. Bradycardia or asystole events are expected to be of very low incidence during this feasibility study.

If the monitor is not disconnected from the SWD 1000 cable prior to using a commercially available portable defibrillator (as may be attempted by emergency responders), there is a remote possibility that some of the portable defibrillator current may be shunted through the SWD 1000 electrodes. Although not directly harmful to the subject, such shunting may reduce the effectiveness of the rescue defibrillation.

It is likely that some subjects will experience a rash due to the adhesive electrodes occluding the skin or sensitivity to the materials used in the construction of the device. In addition, as with all defibrillators, burns are possible if therapy is delivered.

Because defibrillation transfers electricity between the device and the patient, it is theoretically possible for sparking to occur if a gap exists between the therapy pads and the patient. If the spark occurs in an oxygen-rich environment, a fire or explosion may occur. This event has not occurred with the commercially available LifeVest WCD but is a standard warning for all external defibrillators. As the pads

that transfer the electricity from the device to the body are generally under clothing, the risk may be less with the SWD 1000 than with other external defibrillators (no exposure to oxygen-rich surroundings).

There is a possibility that subjects may fail to properly dry the electrode cable as described in the patient manual. In this event, it is possible that the defibrillation circuit completed with the subjects will be shorted and the shock efficacy will be subsequently reduced.

A possible benefit of participating in this study is prompt defibrillation, should the subject have a VT/VF episode. The SWD 1000 is designed to deliver defibrillation treatment within one minute of VT/VF detection, and the median time from arrhythmia onset to shock in commercial use is approximately 45 seconds. Such prompt treatment may therefore be more effective than conventional defibrillation, even in an inpatient setting, because of the time typically required for VT/VF recognition, defibrillator transport to the bedside, application of electrodes, and delivery of a defibrillation pulse by hospital personnel.

This device also allows patients to be discharged from the hospital and to receive follow-up testing on an outpatient basis; doing so may reduce the patient's exposure to hospital-specific hazards.

In some hospital environments, unusually high levels of electromagnetic disturbance could be encountered. Examples of possible sources of such disturbance include: magnetic resonance imaging equipment, communication equipment such as microwave transmitters, arc welding equipment, high voltage transmission lines, electrocautery systems, and electronic muscle stimulators. These high levels of electromagnetic disturbances may cause arrhythmia detections or other device behavior.

8. SUBJECT CONSENT AND CONFIDENTIALITY

Each subject will be informed of the purpose of the investigation, the potential risks and benefits of the study, and the investigational nature of the SWD 1000 prior to their enrollment in the study. The subject must freely sign an IRB approved Informed Consent Form based on template, 90D0119_ICD, prior to any study specific procedures.

Each subject will receive a unique subject identification number. The subject's name and identity will be known to the Investigator and ZOLL (the "Sponsor") but will be kept confidential. Authorized personnel from the ethics committee and regulatory authorities may have access to original subject records.

9. TRIAL DESIGN AND STUDY SIZE

The study is a single arm, open enrollment feasibility study. A maximum of twenty clinical sites will be used to enroll subjects. The multi-site approach is intended to increase variability in the observation of ED characteristics, such as differences in staffing, staff responsibilities, and patient demographic.

A minimum of 50 subjects and a maximum of 80 subjects will be enrolled. The sample size is based on the expected safety objective, which states:

"Specifically, on average monitoring will be inhibited by noise no greater than 2% of the time worn and monitoring using single lead analysis will be no greater than 5% of the time worn."

This objective was taken directly from the LifeVest System Input Requirements (90A0118):

"[R274] Monitoring shall be inhibited by noise no greater than 2% of the time worn on average within the intended patient populations. [R275] Monitoring using single lead analysis shall occur no greater than 5% of the time worn on average within the intended patient populations."

In 2012, the device records of approximately 14,000 patients who used the LifeVest 4000 system were analyzed to determine the system performance. The device records the time when the device is on, when

each of the two ECG channels is determined to be unsuitable for determining the presence of an arrhythmia, and when both leads are determined to be unsuitable. Using these, the time the device was unable to monitor (DUAL) and the time the device was using only a single lead for monitoring (SINGLE) was determined. Each patient's proportion of time spent in SINGLE or DUAL was calculated, then overall descriptive statistics were derived using Excel spreadsheet functions:

	SINGLE	DUAL
Mean	.040	.005
Standard Deviation	.051	.015
Median	.024	.002
Maximum	.762	.644
Minimum	.000	.000
Standard Error	.000431	.000127
95% lower bound	.039989	.004997
95% upper bound	.040011	.005003

The performance of the SWD 1000 is expected to be similar to the 4000 system. A confidence interval of 80% to 90% was used to define expectations of meeting the safety objective for the feasibility stage. A general formula for calculating sample size based on a confidence interval was used:

$$n = \left(2z_{\frac{\alpha}{2}}\sigma/L\right)^2$$

To calculate the sample size for SINGLE performance of the SWD 1000 against the 4000 system:

Confidence: 80%

$$z_{\frac{\alpha}{2}} = 1.28$$

Allowable difference = 0.01 (0.05 permitted, 0.04 is current 4000 performance)

$$L = 0.02$$

Standard deviation = 0.051 (assumed to be similar to the 4000)

$$n = \left(2z_{\frac{\alpha}{2}}\sigma/L\right)^2 = 42$$

Confidence: 90%

$$z_{\frac{\alpha}{2}} = 1.645$$

Allowable difference = 0.01 (0.05 permitted, 0.04 is current 4000 performance)

$$L = .02$$

Standard deviation = 0.051 (assumed to be similar to the 4000)

$$n = \left(2z_{\frac{\alpha}{2}}\sigma/L\right)^2 = 71$$

To calculate the sample size for DUAL performance of the SWD 1000 against the 4000 system:

Confidence: 90%

$$z_{\frac{\alpha}{2}} = 1.645$$

Allowable difference = 0.01 (0.02 permitted, 0.005 is current 4000 performance)
 $L = 0.02$

Standard deviation = 0.015 (assumed to be similar to the 4000)
 $n = \frac{(2z_{\alpha/2}\sigma)^2}{L^2} = 7$

Thus, a sample size of 50 to 80 subjects is expected to demonstrate that both SINGLE and DUAL performance meet the safety objective of the feasibility study.

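### Section 9 says 50 to 80 subjects should demonstrate the signal-quality objective, but a pass on the observed average, though likely, carries no 80–90% confidence that the SINGLE limit is met

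*Combined protocol and SAP*

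**What the plan says.** Section 9 takes its safety objective from a LifeVest system requirement about average performance in the intended patient populations: at most 2% of wear time with no usable lead (DUAL) and at most 5% on a single lead (SINGLE).

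The planning assumption is that "The performance of the SWD 1000 is expected to be similar to the 4000 system". On method, "A general formula for calculating sample size based on a confidence interval was used", namely n = (2zσ/L)², and "A confidence interval of 80% to 90% was used to define expectations of meeting the safety objective for the feasibility stage". For SINGLE the inputs are "Allowable difference = 0.01 (0.05 permitted, 0.04 is current 4000 performance") with L = 0.02, and "Standard deviation = 0.051 (assumed to be similar to the 4000"). The resulting sizes are 42 (SINGLE, 80%), 71 (SINGLE, 90%) and 7 (DUAL, 90%). Enrolment is set accordingly: "A minimum of 50 subjects and a maximum of 80 subjects will be enrolled". The section closes by saying that "a sample size of 50 to 80 subjects is expected to demonstrate that both SINGLE and DUAL performance meet the safety objective".

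Section 6.2.1 gives the success criteria as availability of at least one lead (98% or more of attached time) and of both leads (95% or more), each judged on an average over all patients. It names no confidence limit. Section 13 names none either; it says only that results will be compared with commercial LifeVest use.

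**The concern.** With L = 0.02 the interval is the observed mean ± 0.01, and 0.01 is the entire SINGLE margin. At the formula's own n, the upper limit is at or below 0.05 only when the observed mean is at or below 0.04, the value assumed to be true. The formula controls precision and has no power term, and the plan states no power.

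Section 9 nevertheless moves directly from this interval calculation to the claim that the study should demonstrate a requirement on a population average. Section 6.2.1 then applies a rule without any interval. A reader of the two sections together could take a pass as showing, with 80–90% confidence, that the device meets the 5% limit. This matters because signal quality is the study's surrogate for safety, and Section 10 relies on similar ECG quality for reasonable assurance about the device.

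**Working it through.** **Inputs, all from Section 9.** SINGLE: mean 0.040, SD 0.051, limit 0.05. DUAL: mean 0.005, SD 0.015, limit 0.02. z = 1.28 (80%) and 1.645 (90%). L = 0.02. n = 50 to 80.

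**1. The plan's sizes.** n = (2zσ/L)²:
- SINGLE 80%: (2 × 1.28 × 0.051 / 0.02)² = 42.6 (plan: 42)
- SINGLE 90%: (2 × 1.645 × 0.051 / 0.02)² = 70.4 (plan: 71)
- DUAL 90%: (2 × 1.645 × 0.015 / 0.02)² = 6.1 (plan: 7)

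These reproduce within rounding.

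**2. Standard error and half-width for SINGLE.** SE = 0.051/√n.
- n = 50: SE = 0.00721; 90% half-width 1.645 × SE = 0.0119; 80% half-width 0.0092
- n = 80: SE = 0.00570; 90% half-width 0.0094; 80% half-width 0.0073

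**3. Chance of a SINGLE pass at a true mean of 0.04, normal theory.**
- Written rule (observed mean ≤ 0.05): Φ(0.01/SE)
- Interval rule (upper limit ≤ 0.05): Φ(0.01/SE − z)

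| n | 0.01/SE | Written rule | Upper 80% limit | Upper 90% limit |
|---|---|---|---|---|
| 42 | 1.271 | 90% | 50% | 35% |
| 50 | 1.386 | 92% | 54% | 40% |
| 71 | 1.652 | 95% | 65% | 50% |
| 80 | 1.754 | 96% | 68% | 54% |

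The 50% entries at n = 42 (80%) and n = 71 (90%) follow from setting the half-width equal to the margin.

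**4. Skewness.** The 4000 data are skewed (mean 0.040, median 0.024, maximum 0.762). I simulated 100,000 studies per case with the same mean and SD, under two assumed shapes, for n = 50 to 80:
- Written rule: 91–95% (both shapes)
- Interval rule, lognormal: 53–61% (90% interval), 62–70% (80% interval)
- Interval rule, beta: 45–56% (90% interval), 56–68% (80% interval)

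**5. What a pass under the written rule excludes.** At a true SINGLE mean of exactly 0.05, P(observed mean ≤ 0.05) = Φ(0) = 50% at any n.

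**6. DUAL.** The plan gives "Allowable difference = 0.01 (0.02 permitted, 0.005 is current 4000 performance"), but 0.02 − 0.005 = 0.015, so the half-width of 0.01 is smaller than the margin and the DUAL size is conservative. At n = 50, 0.015/(0.015/√50) = 7.07, so DUAL passes with probability above 99.9% under either rule. SINGLE decides the result.

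**7. The both-leads criterion in Section 6.2.1.** If it limits SINGLE + DUAL, the expected mean is 0.040 + 0.005 = 0.045 and the margin is 0.005. The SINGLE–DUAL correlation is not in the documents. I assume a range of 0 to 1, which gives a combined SD of 0.0532 to 0.066. P(observed mean passes) = Φ(0.005√n/SD):
- n = 50: 75% (correlation 0) to 70% (correlation 1)
- n = 80: 80% (correlation 0) to 75% (correlation 1)

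**The case against.** The strongest defence is that the protocol contains no interval rule. The objective is stated on average, Section 6.2.1 compares an average with the limits, and Section 13 adds no confidence bound. On that rule SINGLE passes 92–96% of the time on the plan's inputs.

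The 80–90% figure is also not misleading as an expectation of passing. The sizing formula gives the chance that the observed mean falls within ± 0.01 of 0.04, which is 2Φ(0.01/SE) − 1: 83% at n = 50 and 92% at n = 80. The one-sided chance of passing is higher still. All of this stands.

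So a reader might infer that the study has only a 40–68% chance of success, or that it is too small. The documents do not support either inference. Those percentages belong to an upper-limit rule that no section adopts, the even-odds result holds only at n = 42 (80%) and n = 71 (90%), and the 40% floor is a normal-theory figure that rises with skewed data. This is also a feasibility study meant to guide later work on definitive safety and efficacy.

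The defence does not rescue the closing sentence of Section 9. That sentence draws a conclusion about demonstration from a confidence-interval calculation, for a requirement on population averages. The rule in Section 6.2.1 can be met without any such confidence.

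**Conclusion.** Wrong as written, and below must-fix. The sample size suits the written rule: about 92–96% for SINGLE, if the SWD 1000 has the 4000's mean and SD. What does not hold is the statement that 50 to 80 subjects should demonstrate the objective, if that is meant in the sense of the interval used for sizing. In that sense the chance is about 40–54% (90% interval) or 54–68% (80% interval) under normal theory, and about 53–61% or 62–70% under an assumed lognormal with the same mean and SD.

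Two limits apply. The equality of half-width and margin is exact for SINGLE only. And 92–96% is for SINGLE alone: if the both-leads criterion limits SINGLE + DUAL, the chance of passing on the average falls to about 70–80%, over assumed correlations of 0 to 1.

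**What to change.** Leave enrolment unchanged, and:

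1. State that the observed all-patient average of Section 6.2.1 decides success, and make Sections 6.2.1, 9 and 13 agree on this.
2. Replace the closing sentence of Section 9, dropping the claim of demonstration. In its place give the 90% half-width for SINGLE (0.0119 at n = 50, 0.0094 at n = 80), the 92–96% chance that the SINGLE average is within its limit, and the 40–54% and 54–68% chances that the upper 90% and 80% limits are within it. State the assumptions: 4000-like mean and SD, normal theory. Label 92–96% as SINGLE alone, and say whether the both-leads criterion applies to SINGLE + DUAL.
3. In Section 13, require the 80% and 90% intervals to be reported beside each average, so that a pass is not read as confidence that the limit is met.

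The cost is wording in three sections, two extra intervals per average in the report, and a less favourable statement of what the study can show.

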10. ANALYSIS OF PROTOCOL

This feasibility study will assess a unique outpatient care model in which syncope patients with cardiac or uncertain etiology, instead of being hospitalized, are provided with, and trained to use, the SWD 1000 prior to discharge from the ED. Only observational data will be collected to assess the logistics of equipping patients with the device and providing training in the ED, and the ability of patients to receive follow care on an outpatient basis. Therefore, the first primary objective where the level of care provided to syncope patients on an outpatient basis is observed is justified. The second primary objective using ECG signal quality as a surrogate for safety is justified because the signal quality relates to both safety (poor ECG quality may lead to inappropriate detections and/or shocks) and efficacy (poor ECG quality may interfere with the detection of a ventricular arrhythmia). In essence, because the detection and treatment sequence of the SWD 1000 is exactly the same as that of previously-approved LifeVest system, demonstrating similar ECG quality will provide reasonable assurance that the device will perform as expected.

The outcomes of this feasibility study will be used to guide the design of future studies in which device functionality enhancements and performance may be further investigated.

11. FORMS AND DATA HANDLING

As with any study, accurate and timely completion of documentation is essential for the successful completion of the trial. The Investigator will be responsible for obtaining and maintaining IRB approved Informed Consent Forms based on template, 90D0119_ICD, and Case Report Forms (90D0119_CRF). A signed copy of the Informed Consent Form will be given to every subject. A copy of each Case Report Form will be sent to the Sponsor, with the originals maintained by the Investigator.

12. ADVERSE EVENTS

The Investigator will be responsible for recording all adverse device effects regardless of causality on the Case Report Form. Serious adverse events include any event that is fatal or life threatening, requires or prolongs hospitalization, or is permanently disabling. The Investigator will assess whether the adverse event is anticipated or unexpected. An unexpected adverse event is any adverse event not identified by nature, severity or frequency prior to the investigation. Anticipated events include, but are not limited to:

- Skin rash or irritation is commonly associated with adhesive electrode use.
- Burns are common after a defibrillation shock.
- Inappropriate shocks from supraventricular tachycardia, t-wave misclassification or other forms of “double counting”, or electrical interference (with the outpatient device, this occurs at a rate of about 1 per 100 months of use).
- Inappropriate shocks may induce a ventricular arrhythmia at a rate of about 1 per 100 inappropriate shocks.

- Alarms may awaken patients at night.
- Discomfort may arise from device placement.
- Some shunting of current may result if the SWD 1000 is not disconnected prior to a defibrillation. This may result in less effective defibrillation and possibly death.

The investigational device exemption (IDE) regulations define an unanticipated adverse device effect (UADE) as "any serious adverse effect on health or safety or any life-threatening problem or death caused by, or associated with, a device, if that effect, problem, or death was not previously identified in nature, severity, or degree of incidence in the investigational plan or application (including a supplementary plan or application), or any other unanticipated serious problem associated with a device that relates to the rights, safety, or welfare of subjects" (21 CFR 812.3(s)). UADEs must be reported by the clinical investigator to the sponsor and the reviewing IRB, as described below:

- For device studies, investigators are required to submit a report of a UADE to the sponsor and the reviewing IRB as soon as possible, but in no event later than 10 working days after the investigator first learns of the event (§ 812.150(a)(1)).
- Sponsors must immediately conduct an evaluation of a UADE and must report the results of the evaluation to FDA, all reviewing IRBs, and participating investigators within 10 working days after the sponsor first receives notice of the effect (§§ 812.46(b), 812.150(b)(1)).

The IDE regulations, therefore, require sponsors to submit reports to IRBs in a manner consistent with the recommendations made above for the reporting of unanticipated problems under the investigational new drug (IND) regulations.

13. STATISTICAL DATA ANALYSIS PLAN

Data from all subjects enrolled in the study will be considered and/or analyzed. All appropriate data stored in the monitor during the time the SWD 1000 is worn will be analyzed and may be correlated with arrhythmias. The data stored in the monitor includes:

- Automatically stored ECG recordings (including true arrhythmias and false arrhythmia declarations).
- Manually stored ECG recordings.
- Duration of time that the SWD 1000 was worn.
- Noise, arrhythmia, and other internal event flags.
- Device actions during a treatment sequence; i.e., transthoracic impedance measurement, energy delivered and outcome.
- Subject device interactions, including subject use of the response buttons.

If an event occurs, the stored data will be analyzed. The data will also be analyzed to determine frequency of noise events, frequency of false arrhythmia events, and percentage of subject wear time. The results obtained will be compared with the results of commercial LifeVest use.

14. ADMINISTRATIVE RESPONSIBILITIES

ZOLL, the Sponsor, is responsible for study administration and providing devices and related materials for the study. At the conclusion of the study, the Investigators will return all SWD 1000 units to the Sponsor.

The Sponsor will designate one or more appropriately trained and qualified individuals to monitor the investigation. These individuals will conduct at least one pre-investigation on-site visit and one on-site visit per site during the investigation to verify the adherence to procedures specified in the protocol, and verify maintenance of required subject and data records. Monitoring activities will be conducted according to ZOLL's Monitoring of Clinical Studies Standard Operating Procedures and will be documented.

The Investigator is responsible for obtaining and maintaining ethics approval of the study protocol for their site. The Investigator is responsible for obtaining patient consent, and maintaining Informed Consent Forms and Case Report Forms for each subject. The Investigator is responsible for reporting and maintaining records of study protocol deviations and all IRB correspondence and other significant correspondence relating to the study. At the conclusion of the study, the Investigator will provide a report to the ethics committee.

If the device malfunctions or fails to function as expected, the Investigator must report the incident to ZOLL immediately.

Patient identities will be kept confidential; however, ZOLL may provide study results to the USA's Food and Drug Administration (FDA) and other regulatory agencies.

REFERENCES

5. Huff, J.S. *et al.* Clinical policy: critical issues in the evaluation and management of adult patients presenting to the emergency department with syncope. *Ann Emerg Med* **49**, 431-444 (2007).
